7.3 Dose modifications and management of investigational product-related toxicities

Guidelines for the management of hematological and non-hematological AEs for AZD1775 and CBDP are described below.

Toxicity will be assessed utilizing the NCI Common Terminology Criteria for Adverse Event (CTCAE) version 4.03 unless otherwise specified.

Dose adjustments will be based on the organ system exhibiting the greatest degree of toxicity. Dose reductions or holds and initiation of supportive care are allowed as clinically indicated by the treating physician. Any patient requiring a toxicityrelated- dose delay of more than 28 days from the intended day of the next scheduled dose must be discontinued from the study unless there is approval from the Study Physician for the patient to continue. If Day 1 treatment with either AZD1775 or CBDP is interrupted, then both study medications will be

delayed until the combination can be resumed. See [Appendix B Table](#) and [Appendix B Table](#) for dose level reductions.

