4.9.2 Assessments following discontinuation of investigational product

Patients who are permanently discontinued from receiving IP will remain in the study and will be followed per the study plan (see the relevant arm sub-protocol) for safety, including the collection of any protocol-specified blood specimens, unless consent is withdrawn or the patient is lost to follow-up or enrolled in another clinical study. All patients will be followed for survival (please see follow-up tables for each specific study arm). Patients who decline to return to the site for evaluations will be offered follow-up by phone. However, patients who discontinue due to an AE will need to attend all protocol-specified visits, and all assessments will be conducted as scheduled.

All patients who have any Grade 3 or 4 laboratory values at the time of discontinuation must have further tests performed, and the results must be recorded on the appropriate electronic case report form (eCRF) until the laboratory values have returned to Grade 1 or 2, unless these values are not likely to improve because of the underlying disease.

At discontinuation, all ongoing study-related toxicities and serious adverse events (SAEs) must be followed until resolution unless, in the Investigator's opinion, the condition is unlikely to resolve due to the patient's underlying disease.

All SAEs occurring for up to the pre-defined time period after the last dose of study treatment must be recorded in the eCRF. See the relevant appendices for the pre-defined time period for collection of SAEs for specific agents.

Drug- or study procedure-related SAEs must be captured until the patient completes the follow-up period following discontinuation of study drug (due to confirmed progression of disease) or is permanently withdrawn from the study. Both the patient and the physician will be asked about the subsequent treatment the patient receives during the follow-up period per the study plan.

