Appendix B Table 8 Hematologic dose modifications and management

Neutrophil and Platelet Blood Counts and Study Drug Action								
Neutrophil count	Action AZD1775	Action chemo	2nd event	Action AZD1775	Action chemo	3rd event	Action AZD1775	Action chemo
Grade 2 <1.5-1.0 $\times 10^9/L$	Hold Resume at same dose	Hold Resume at same dose		Hold Resume at DL-1	Hold Resume at same dose		Hold Resume at DL-2	Hold Resume at DL-1
Grade 3 <1.0-0.5 $\times 10^9/L$	Hold Resume at DL-1	Hold Resume at same dose		Hold Resume at DL-2	Hold Resume at DL-1		Hold Resume at DL-2	Hold Resume at DL-2

Neutrophil and Platelet Blood Counts and Study Drug Action

Grade 3 <1.0-0.5 x10 ⁹ /L with documented infection and/or fever	Hold Resume at DL-1	Hold Resume at DL-1		Hold Resume at DL-2	Hold Resume at DL-2		Hold Contact Medical Monitor	Hold Contact Medical Monitor
Grade 4 <0.5 x10 ⁹ /L	Hold Resume at DL-1	Hold Resume at DL-1		Hold Resume at DL-2	Hold Resume at DL-2		Discontin ue and follow for disease progressi on	Discontin ue and follow for disease progression
Grade 4 Febrile neutropenia or Grade 4 Infection with neutropenia	Discontin ue and follow for disease progressi on	Discontin ue and follow for disease progressi on						
Platelet count	Action AZD177 5	Action chemo	2nd event	Action AZD177 5	Action chemo	3rd event	Action AZD177 5	Action chemo
Grade 2 75,000- 50,000/ μ L	Hold Resume at same dose	Hold Resume at same dose		Hold Resume at DL-1	Hold Resume at same dose		Hold Resume at DL-1	Hold Resume at DL-1
Grade 3 50,000- 25,000/ μ L	Hold Resume at DL-1	Hold Resume at same dose		Hold Resume at DL-2	Hold Resume at DL-1		Hold Resume at DL-2	Hold Resume at DL-2
Grade 4 <25,000/ μ L without any evidence of bleeding	Hold Resume at DL-1	Hold Resume at DL-1		Hold Resume at DL-2	Hold Resume at DL-2		Discontin ue and follow for disease progressi on	Discontin ue and follow for disease progression
Thrombocy topenic haemorrhag e (gross occult bleeding) associated with platelet count <50,000/ μ L	Discontin ue	Discontin ue						

Neutrophil and Platelet Blood Counts and Study Drug Action

^a If hematologic toxicity parameters do not recover within 28 days, the patient should be removed from the study treatment.

ANC Absolute neutrophil count

Please consider using G-CSF in the event of severe neutropenia or febrile neutropenia according to institutional standards.

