No more than two dose reductions will be allowed for any patient. Patients requiring further dose reduction due to toxicity must discontinue study treatment. Dose re-escalation is not allowed. If the patient has concurrent neutropenia and thrombocytopenia, please follow the most conservative guidance in the table below and discuss with Medical Monitor AstraZeneca Study Physician as needed.

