8.4.1 Dose Reduction: Ceralasertib + Olaparib Combination

For ceralasertib, study treatment can be dose reduced according to the following dose modification table. A maximum of 2 dose reduction steps are permitted. If after the second dose reduction treatment is not tolerated, no further dose reduction is allowed, and study treatment should be discontinued. Dose re-escalation is not permitted. Further dose modifications are described in Appendix C Table 5 below.

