Appendix C Table 5 : Cohort C Guidance for dose reductions for ceralasertib and olaparib*

Dose Level	Ceralasertib	Olaparib
Initial dose level	160 mg QD Days 1-7	300 mg BID Days 1-28
1 st dose reduction	Dose reduce either AZD6738 or Olaparib or Both	
Haematological Toxicity	160mg QD Days 1-4	250 mg BID Days 1-28
Non-Haematological Toxicity	120mg QD Days 1-7	250 mg BID Days 1-28
2nd dose reduction	Dose reduce either Ceralasertib or Olaparib or Both	
	120 mg QDQ Days 1-4	200 mg BID Days 1-28
3 rd dose reduction: No further reduction permitted, withdraw patient and treat as clinically indicated. Dose must not be re-escalated even if toxicities have resolved in subsequent cycles.		

* Ceralasertib and olaparib may be reduced stepwise within each dose reduction level e.g., dose reduce olaparib first followed by ceralasertib if the AE recurs. Dose reductions for anaemia should occur for olaparib first (with consideration to a simultaneous dose reduction in ceralasertib depending on the severity, duration and recurrence of the anaemia). If a dose reduction is required for neutropenia, leukopenia and thrombocytopenia, olaparib and ceralasertib should be dose reduced simultaneously as there is a greater frequency associated with ceralasertib. For a second dose-reduction, follow the guidance above on which of either, or both agents, to dose-reduce depending on the observed toxicity.

Appendix C Table 8 provides guidance for hematologic toxicity (neutropenia, leukopenia and thrombocytopenia) observed any time during the study treatment period. **For Day 1 of each cycle please check the required blood counts to commence treatment in Appendix C Table 6.**

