8.4.2 Management of Haematological Toxicities for Ceralasertib and Olaparib Combination

Complete blood counts will be obtained for all patients at the beginning of each treatment cycle (Day 1) and should be checked by the Investigator prior to dosing the patient. If haematologic toxicity occurs treatment should be modified as below (Appendix C Table 6), and ANC and platelets should be monitored weekly (more often as clinically indicated until recovery). If haematologic parameters do not recover within 28 days, the patient should be removed from the study treatment.

Appendix C Table 6: Day 1 Haematologic dose modifications and management for ceralasertib plus olaparib combination

Treatment day blood counts and toxicity			
ANC		Platelets	Action
≥1500/μL	And	≥100,000/μL	No dose modification or interruption
<1500/μL	Or	<100,000/μL	Delay by 1week intervals until recovery

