8.4.2.4 Management of non-haematological toxicity for ceralasertib and olaparib

Acute toxicities in the all treatment arms should be managed as medically indicated, with temporary suspension of IP and initiation of supportive care as clinically indicated by the treating physician. Treatment must be interrupted if any NCI-CTCAE Grade 3 or 4 non hematologic AE occurs which the Investigator considers to be related to the administration of the study treatment(s). Treatment should not be restarted until the toxicity has resolved to Grade \leq 1.

Repeat dose interruptions are permitted, for a maximum of 28 days. Any patient who develops a Grade 3 or 4 non-haematologic toxicity that does not resolve to \leq Grade 1 within this period, should be removed from the study treatment. Once a dose is reduced, re escalation is not permitted.

A summary of the dose reduction guidance for ceralasertib and olaparib is presented earlier.

At the first occurrence of CTCAE grade 3 and 4 non-haematological toxicity, ceralasertib and olaparib should be held until resolution of toxicity. At the resolution of the first occurrence of any of these toxicities, no change must be made to dose. At the second occurrence, upon resolution of toxicity, ceralasertib and/or olaparib should be reduced by the 1st dose reduction for non-haematological toxicity to 120 mg qd for 7 days and/or olaparib 250 mg BID q 12 hours daily ([Appendix C Table 5](#) and [Appendix C Table 9](#)) Despite this change, at the third occurrence, upon resolution of toxicity, ceralasertib and/or olaparib should be reduced by the 2nd dose reduction to 120 mg qd for 4 days and 200 mg bid q 12 hours daily ([Appendix C Table 5](#) and [Appendix C Table 9](#)). If despite these changes, there is a fourth occurrence of toxicity, the patient should permanently discontinue study drug. Please note that, for each dose reduction, the investigator may choose to reduce ceralasertib or olaparib or both drugs. If only one drug is dose reduced, the second drug may be reduced as an additional step. Refer to [Appendix C Table 9](#) for specific dose modification guidance regarding non-haematological toxicity.

Appendix C Table 9: Summary of guidance on the management of non-haematologic toxicity for ceralasertib and olaparib

Toxicity	Ceralasertib and olaparib

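### Arms B and C say a toxicity delay of more than 28 days ends study participation, against master text that ends treatment only; read literally, this could stop scans before a response is confirmed.

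*Protocol*

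**What the plan says.** **Leaving the study.** Appendix B 7.3 and Appendix C 8.4 use the same wording. A patient with a toxicity-related delay of more than 28 days from the intended day of the next dose "must be discontinued from the study unless there is approval from the Study Physician for the patient to continue". For a third dose reduction, Appendix C Table 5 reads "No further reduction permitted, withdraw patient and treat as clinically indicated".

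**Leaving treatment only, in the same appendices.**
- Arm B, haematological toxicity not recovered in 28 days (Table 8, footnote a): "the patient should be removed from the study treatment".
- Arm B, Grade 3 or 4 non-haematological toxicity not resolved in 28 days (7.3.2): discontinued from study treatment, and the other drug may continue if only one is to blame.
- Arm B, more than two reductions needed (text after Table 8): "Patients requiring further dose reduction due to toxicity must discontinue study treatment".
- Arm C, haematological toxicity (8.4.2): "If haematologic parameters do not recover within 28 days, the patient should be removed from the study treatment".
- Arm C, after the second reduction (8.4.1): "no further dose reduction is allowed, and study treatment should be discontinued".
- Arm C, fourth non-haematological occurrence (8.4.2.4): "the patient should permanently discontinue study drug".

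**Master protocol.** Section 4.9.2 states: "Patients who are permanently discontinued from receiving IP will remain in the study and will be followed per the study plan". Section 4.9.1 continues scheduled tumour assessments for anyone who stops treatment for a reason other than progression, until confirmed progression or death, unless consent is withdrawn. Section 6.1 names toxicity discontinuations explicitly and has them scanned to progression or death and followed for survival.

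**The concern.** For overlapping events, the documents give two different outcomes: the patient leaves the study, or leaves treatment and stays in follow-up. The arm rule is worded as an obligation and sits in the appendix that a site uses to manage toxicity, so it may be applied as written.

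What is at stake is the scan record. Section 9.4.1.2 requires a response to be confirmed by repeat imaging at least 4 weeks after it is first seen. A patient with a first partial response who is taken off study before the next scan cannot be confirmed. Section 9.5.2 makes the Full Analysis Set the primary population for ORR, and 9.3.1 puts every treated patient in it, so this patient stays in the denominator as a non-responder. PFS would be censored at the last evaluable scan, and under 9.4.1.3 a progression or death after two or more missed visits is censored there too. Because the trigger is prolonged toxicity, that censoring would not be independent of how the patient is faring.

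**Working it through.** The plan states no figure on this point. The check compares passages and then looks at visit timing.

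**1. Does off study end imaging?** Master 6.1 collects images until confirmed progression or until the patient is taken off study. Appendix B 6.3 and Appendix F 4.1 have the same alternative end point. An instruction to discontinue from the study therefore meets a written end point for imaging, although 4.9.1, another paragraph of 6.1 and Appendix B Table 1 continue scans to progression or death.

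**2. Does master 4.10 resolve it?** Section 4.9.1 sends patients withdrawn from the study to 4.10. That section deals with screen failure, withdrawal of consent and survival status for withdrawn or lost patients. A treated patient removed for toxicity, with consent intact, fits none of these.

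**3. Can the rule act between first response and confirmation?** Take the second cycle as the delayed one, with first dose on Day 1.

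| | Arm B | Arm C |
|---|---|---|
| Cycle 2 due | 1 + 21 = Day 22 | 1 + 28 = Day 29 |
| 28-day limit reached | 22 + 28 = Day 50 | 29 + 28 = Day 57 |
| First scan (nominal) | Week 6: 1 + 42 = Day 43 | Week 8: 1 + 56 = Day 57 |
| Earliest confirmation (+28 days) | Day 71 | Day 85 |
| Next scheduled scan (Week 12) | 1 + 84 = Day 85 | Day 85 |

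Master section 5 keeps scan dates fixed when doses are delayed, so these days stand. In both arms the limit can pass after, or at, the first scan and before the confirming one.

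**4. Effect of one lost confirmation on ORR** (1/n, all treated patients in the denominator):
- n=10: 1/10 = 10 points. At stage 1, 1/10 would become 0/10, which 2.2.1 gives as its example of no benefit leading to an early stop.
- n=20: 1/20 = 5 points. For illustration, 3/20 = 15% (exact 95% CI 3.2 to 37.9) becomes 2/20 = 10% (1.2 to 31.7).
- n=40: 1/40 = 2.5 points.

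**5. How many patients?** The documents give no rate of delays beyond 28 days. The Grade 3 or higher neutropenia rate quoted in Appendix B 2.4.2 (35.6%) comes from a regimen that also contained paclitaxel, had a comparator rate of 33.3%, and is not a delay rate. No expected bias can be computed.

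**The case against.** The strongest reply is that this is loose drafting and that the explicit follow-up rules already settle it. Master 4.9.1 and 6.1 cover toxicity discontinuations directly. Appendix B Table 1 schedules scans to confirmed progression or death. Appendix C 6.3 and 7.3 follow patients to progression, and 7.3 adds survival follow-up whether or not treatment is stopped or delayed. The Study Physician can also approve continuation. All of this stands, and it shows which way the conflict is likely to be resolved. It does not remove the conflict. The arm rule is mandatory in form, and the physician's approval is discretionary and concerns continuing, so it secures nothing for patients who are not approved.

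The reply is also right that exposure is narrow. In Arm B, removal comes more than 21 + 28 = 49 days after the last Day 1, against scans every 42 days. A response seen before the last dose would normally be rescanned first. Only a response first seen during the hold is at risk.

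Three stronger readings are tempting, and the documents do not support them:
- **Survival follow-up stops.** Section 4.9.1 follows all patients for survival to the end of the study. Section 4.10.2 keeps it even after consent withdrawal unless it is expressly refused. The re-check in 4.10.3 covers every patient in the full analysis set; consent withdrawals and losses to follow-up are named as included, not as the only ones.
- **Arm B removes patients from the study at a third reduction.** Its text stops study treatment only, and Table 8 has patients followed for disease progression after a third Grade 4 event.
- **Arm C clearly does so.** That rests on one table cell that does not say from what the patient is withdrawn, while 8.4.1 says study treatment.

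**Conclusion.** The contradiction is real. Appendix B 7.3 and Appendix C 8.4 conflict with master 4.9 to 4.9.2 and 6.1 and with the treatment-only rules in the same appendices. Appendix C Table 5 is ambiguous against 8.4.1. The consequence is a risk to scans, and through them to confirmed ORR and PFS. It depends on a site applying the arm rule literally, on the Study Physician not approving continuation, and on a first response falling inside the hold. The risk is clearest in Arm B, whose own efficacy section ends imaging when a patient is off study; Arm C 6.3 and 7.3 point the other way. Each such patient would cost 10 points of ORR at n=10 and 5 points at n=20. These figures illustrate scale and do not estimate expected bias. They take the Full Analysis Set as the denominator, as 9.5.2 does.

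**What to change.** Reconcile Appendix B 7.3, Appendix C 8.4 and the third-reduction entry of Appendix C Table 5 with master 4.9 to 4.9.2 and 6.1, and with the treatment-only wording in Appendix B Table 8 and 7.3.2 and Appendix C 8.4.1, 8.4.2 and 8.4.2.4. In each of the three places, add a sentence that a patient whose study treatment ends for toxicity remains in the study for scheduled tumour assessments until progression or death, and for survival follow-up per 4.9.1, 4.9.2 and 6.1, unless consent is withdrawn. Word it so that it does not disturb the provision in Appendix B 7.3.2 that the remaining drug may continue.

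The rule for when treatment stops, and the Study Physician's role in it, are left to the sponsor and are unchanged by this edit. The cost is wording in three places and, for the few patients affected, some scans that are already on the schedule.

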Appendix B Table 6 AZD1775 dose level reductions for toxicity

AZD1775 Starting Dose^a	AZD1775 -1 level	AZD1775 -2 level
225 mg BID (5 doses over 2.5 days)	175 mg BID (5 doses over 2.5 days)	125 mg BID (5 doses over 2.5 days)

^a AZD1775 twice daily taken in 12 hour intervals over 2.5 days on Days 1-3
BID twice daily

Appendix B Table 7 CBDP dose level reductions for toxicity

CBDP Starting Dose^a	CBDP -1 level	CBDP -2 level
AUC 5	AUC 4	AUC 3

^a CBDP is administered on Day 1 of each 21-day cycle.
AUC Area under the plasma drug concentration-time curve; CBDP carboplatin

7.3.1 Dose modifications due to hematologic-related adverse events

Hematologic panel (complete blood counts, 5-part differential [neutrophils, lymphocytes, monocytes, basophils and eosinophils], and platelets) will be obtained for all patients **at the beginning of each treatment cycle (Day 1) and reviewed prior to dose administration**. If hematologic toxicity occurs ([Appendix B Table 8](#)), treatment should be held and ANC and platelets should be monitored at least weekly until recovery. Patients should be managed as medically indicated. Treatment should not be resumed **until recovery to Grade 1** (ANC $\geq 1.5 \times 10^9/L$ or 1,500/ μL ; platelets $\geq 75,000/ \mu L$).

Appendix B Table 8 Hematologic dose modifications and management

Neutrophil and Platelet Blood Counts and Study Drug Action								
Neutrophil count	Action AZD1775	Action chemo	2nd event	Action AZD1775	Action chemo	3rd event	Action AZD1775	Action chemo
Grade 2 <1.5-1.0 $\times 10^9/L$	Hold Resume at same dose	Hold Resume at same dose		Hold Resume at DL-1	Hold Resume at same dose		Hold Resume at DL-2	Hold Resume at DL-1
Grade 3 <1.0-0.5 $\times 10^9/L$	Hold Resume at DL-1	Hold Resume at same dose		Hold Resume at DL-2	Hold Resume at DL-1		Hold Resume at DL-2	Hold Resume at DL-2

Neutrophil and Platelet Blood Counts and Study Drug Action

Grade 3 <1.0-0.5 x10 ⁹ /L with documented infection and/or fever	Hold Resume at DL-1	Hold Resume at DL-1		Hold Resume at DL-2	Hold Resume at DL-2		Hold Contact Medical Monitor	Hold Contact Medical Monitor
Grade 4 <0.5 x10 ⁹ /L	Hold Resume at DL-1	Hold Resume at DL-1		Hold Resume at DL-2	Hold Resume at DL-2		Discontin ue and follow for disease progressi on	Discontin ue and follow for disease progression
Grade 4 Febrile neutropenia or Grade 4 Infection with neutropenia	Discontin ue and follow for disease progressi on	Discontin ue and follow for disease progressi on						
Platelet count	Action AZD177 5	Action chemo	2nd event	Action AZD177 5	Action chemo	3rd event	Action AZD177 5	Action chemo
Grade 2 75,000- 50,000/ μ L	Hold Resume at same dose	Hold Resume at same dose		Hold Resume at DL-1	Hold Resume at same dose		Hold Resume at DL-1	Hold Resume at DL-1
Grade 3 50,000- 25,000/ μ L	Hold Resume at DL-1	Hold Resume at same dose		Hold Resume at DL-2	Hold Resume at DL-1		Hold Resume at DL-2	Hold Resume at DL-2
Grade 4 <25,000/ μ L without any evidence of bleeding	Hold Resume at DL-1	Hold Resume at DL-1		Hold Resume at DL-2	Hold Resume at DL-2		Discontin ue and follow for disease progressi on	Discontin ue and follow for disease progression
Thrombocy topenic haemorrhag e (gross occult bleeding) associated with platelet count <50,000/ μ L	Discontin ue	Discontin ue						

Neutrophil and Platelet Blood Counts and Study Drug Action

^a If hematologic toxicity parameters do not recover within 28 days, the patient should be removed from the study treatment.

ANC Absolute neutrophil count

Please consider using G-CSF in the event of severe neutropenia or febrile neutropenia according to institutional standards.

No more than two dose reductions will be allowed for any patient. Patients requiring further dose reduction due to toxicity must discontinue study treatment. Dose re-escalation is not allowed. If the patient has concurrent neutropenia and thrombocytopenia, please follow the most conservative guidance in the table below and discuss with Medical Monitor AstraZeneca Study Physician as needed.

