7.3.2 Dose modifications due to non-hematologic related adverse events

Dose modifications for non-hematologic toxicities should be based on toxicities occurring during the previous cycle. For toxicities that lead to a dose reduction, the dose will not be re-escalated during subsequent cycles.

Any patient who develops a Grade 3 or 4 non-hematologic toxicity that does not resolve to \leq Grade 1 within 28 days should be discontinued from the study treatment. However, if the Investigator determines that the non-hematologic toxicity was due to one study drug and not the other, treatment with the remaining study drug may continue as clinically appropriate.

Based upon the maximum non-hematologic toxicities experienced during the previous cycle, dose adjustments for subsequent cycles are to be made according to the criteria defined in [Appendix B Table 9](#) (unless specified per unique toxicities as noted below).

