Appendix B Table 9 Non-hematologic toxicity dose modification and management

Electrocardiogram QT corrected interval prolonged		
QTc Value	CBDP	AZD1775
QTc 450-480 ms (males) or 470-480 (females)	No dose modifications	Hold. Once QTc interval has returned to pretreatment status and correction of possible electrolyte imbalance has been made, resume at next lower dose level.
QTc 481-500 ms	No dose modifications	Hold. Seek cardiologist advice.

QTc \geq 501 ms	Discontinue treatment	Discontinue treatment
Shift from baseline of \geq 60ms	Discontinue treatment	Discontinue treatment
<hr/>		
CTCAE version 4.03	CBDP	AZD1775
Grade 0 - 2	No dose modification	No dose modification
Grade 3 ^{b,c,d}	Hold ^a	Hold ^a
Grade 4 ^b	Hold until toxicity resolves to Grade \leq 1. Resume with 1 dose level reduction	Hold until toxicity resolves to Grade \leq 1. Resume with 1 dose level reduction
Second repeat incidence of Grade 3 or 4 toxicity (except nausea, vomiting, fatigue, malaise, lethargy, anorexia, alopecia)	Discontinue treatment	Discontinue treatment
<hr/>		
Hepatic		
<hr/>		
CTCAE v4.03	CBDP	AZD1775
Grade 1-2	No dose modification	No dose modification
Grade 3 or 4 (manifested as elevations in ALT, AST, ALP, or bilirubin)	Hold until resolves to Grade \leq 1 or baseline, then resume CBDP with a 1 level dose reduction. If not resolved within 28 days, discontinue CBDP.	Hold until resolves to Grade \leq 1 or baseline, then resume study drug with a 1 level dose reduction. If not resolved within 28 days, discontinue study drug.
<hr/>		
Diarrhea or mucositis		
<hr/>		
CTCAE v4.03	CBDP	AZD1775
Grade 1-2	No dose modification	No dose modification
Grade 3 or 4 (or requiring hospitalization)	Hold ^a	Hold ^a
<hr/>		
Nephrotoxicity		
<hr/>		
CTCAE v4.03	CBDP	AZD1775
Grade 0-1	No dose modification	No dose modification

Grade ≥ 2 Hold until resolves to Grade ≤ 1 or Hold^a
baseline, then resume CBDP with
a 1 level dose reduction. If not
resolved within 28 days,
discontinue CBDP.

Neurotoxicity		
CTCAE v4.03	CBDP	AZD1775
Grade 1	No dose modification	No dose modification
Grade 2	Hold until toxicity resolves to Grade ≤ 1 . Resume with 1 dose level reduction.	No dose modification
Grade 3 or 4	Discontinue treatment	Discontinue treatment

- ^a Hold until toxicity resolves to \leq Grade 1 and then resume at the same dose with no modification.
- ^b Dose reduction for nausea and vomiting should be made only if Grade 3 or Grade 4 toxicity occurs in spite of maximum anti-emetics.

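### Arm B Table 8 can send a patient already at DL-2 back to DL-1, which the same section forbids, and no rule says what to do instead

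*Protocol*

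**What the plan says.** Appendix B Table 6 gives AZD1775 a starting dose of "225 mg BID (5 doses over 2.5 days)", a -1 level of "175 mg BID (5 doses over 2.5 days)" and a -2 level of "125 mg BID (5 doses over 2.5 days)". Table 7 does the same for carboplatin: AUC 5, then AUC 4, then AUC 3.

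Table 8 (hematologic toxicity) has one row per cell line and grade, and columns for a first, second and third event. Each cell tells the site to hold and then resume at the same dose, at DL-1 or at DL-2, to contact the medical monitor, or to discontinue. It does not say whether events are numbered within a row, within a cell line or overall.

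The text of Section 7.3.1 that goes with Table 8 adds two limits: "No more than two dose reductions will be allowed for any patient", with discontinuation if more is needed, and "Dose re-escalation is not allowed". For neutropenia and thrombocytopenia that occur together, it asks for the more conservative guidance.

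Section 7.3.2 repeats the ban for non-hematologic toxicity: "the dose will not be re-escalated during subsequent cycles". Table 9, however, works in steps from the current dose; its QTc row, for example, says "resume at next lower dose level".

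**The concern.** Tables 6 and 7 give DL-1 and DL-2 as fixed doses, and most Table 8 cells name one of them without asking where the patient already is. A patient at DL-2 who has a different kind of hematologic event can therefore be directed to DL-1, a higher dose, straight after a toxicity. The text forbids this but does not say what replaces the cell.

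Sites could then handle the same patient differently in a myelosuppressive combination. That bears first on safety. It also bears on the Arm B summaries of exposure, delays and dose reductions planned in master protocol Section 9.5.4, which would partly reflect how each site read the table.

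**Working it through.** **Inputs.** Seven rows of Table 8 have entries for repeat events. DL-1 and DL-2 are taken as the -1 and -2 levels of Tables 6 and 7. Same dose is read as the patient's current dose, the reading most favourable to the protocol. Entries are AZD1775 / carboplatin:

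| Row | 1st event | 2nd event | 3rd event |
|---|---|---|---|
| Neutrophils G2 | same / same | DL-1 / same | DL-2 / DL-1 |
| Neutrophils G3 | DL-1 / same | DL-2 / DL-1 | DL-2 / DL-2 |
| Neutrophils G3 with infection or fever | DL-1 / DL-1 | DL-2 / DL-2 | contact monitor |
| Neutrophils G4 | DL-1 / DL-1 | DL-2 / DL-2 | discontinue |
| Platelets G2 | same / same | DL-1 / same | DL-1 / DL-1 |
| Platelets G3 | DL-1 / same | DL-2 / DL-1 | DL-2 / DL-2 |
| Platelets G4 | DL-1 / DL-1 | DL-2 / DL-2 | discontinue |

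**Paths.** Three events give 7 × 7 × 7 = 343 paths; two events give 7 × 7 = 49. A path conflicts with the ban when the named level is a higher dose than the current one. The highest dose any cell names is DL-1, so this requires a drug already at DL-2.

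**Two events.** After one event neither drug is below DL-1, so 0 of 49 paths conflict.

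**Three events, counted overall.**
- Third event G2 platelets (names DL-1 for both drugs): AZD1775 is at DL-2 if the second event was in any of five rows, so 7 × 5 = 35 paths. In 7 × 3 = 21 of these, carboplatin is at DL-2 too.
- Third event G2 neutrophils (names DL-1 for carboplatin): carboplatin is at DL-2 after three possible second events, so 7 × 3 = 21 paths.
- Total 35 + 21 = 56 of 343 (16%): AZD1775 in 35, carboplatin in 42.

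**Three events, counted per cell line.**
- All neutrophil, ending in G2: 4 × 2 = 8 (carboplatin).
- All platelet, ending in G2: 3 × 2 = 6 (AZD1775; carboplatin also in 3).
- Two neutrophil events, then a first G3 or G4 platelet event: 12 × 2 = 24 (AZD1775; carboplatin also in 8).
- Two platelet events, then a first neutrophil event of G3, G3 with infection or fever, or G4: 6 × 3 = 18 (AZD1775; carboplatin also in 6).
- Total 8 + 6 + 24 + 18 = 56 of 343: AZD1775 in 48, carboplatin in 25.

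**Three events, counted per row.** AZD1775 reaches DL-2 only after two events in the same one of five rows. A first event in any of the other four then names DL-1: 5 × 4 = 20 of 343 (6%). Carboplatin rises as well in 3 × 2 = 6 of these.

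**Examples.**
- Per row: two G3 neutropenias put AZD1775 at 125 mg BID; a first G4 neutropenia names 175 mg BID (175/125 = 1.40, +40%).
- Overall or per cell line: G2 then G4 neutropenia puts carboplatin at AUC 3; a third event of G2 neutropenia names AUC 4 (4/3 = 1.33, +33%).
- Across tables: two one-step AZD1775 reductions under Table 9, one for QTc and one for a hepatic event, lead to 125 mg BID; a first G3 neutropenia then names 175 mg BID. Only one hematologic event is needed.

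**Can DL-1 and DL-2 mean steps down from the current dose?** No. In the G3 neutrophil row the AZD1775 entries DL-1, DL-2, DL-2 would add up to 1 + 2 + 2 = 5 steps, and only two levels exist. The fixed reading is the workable one, and it is the one that meets the ban.

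**The case against.** The strongest reply is that every conflicting path involves a drug already at the lowest level, and that Section 7.3.1 speaks to exactly that patient: no re-escalation, no more than two reductions, and discontinuation if a further reduction is needed. Those sentences belong to the same section as Table 8, so a careful site would not raise the dose. This largely stands as regards the increase itself. A reader might infer that the protocol permits re-escalation or that patients will be dosed up; the documents do not support that.

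It does not settle what the site should do. No precedence between text and table is stated. The instruction to take the more conservative guidance covers concurrent cytopenias, not successive ones. Table 8 itself contains both outcomes for a patient at AZD1775 DL-2: a third G3 neutropenia keeps DL-2, a third G4 neutropenia discontinues.

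Other stronger readings also fail:
- **A patient frequency.** Appendix B Section 2.4.2 reports Grade 3 or higher neutropenia in 35.6% and thrombocytopenia in 20.3%, and multiplying them is tempting. One event of each by itself triggers nothing, and those rates come from a triplet with paclitaxel in ovarian cancer.
- **Table 8 never looks at the current level.** The same-dose cells do.
- **The dose always rises after a worse toxicity.** Under overall counting, all 56 paths end in a Grade 2 event.
- **Table 9's step wording is itself an error.** Naming steps in one table and levels in another is not a contradiction, and Section 7.3 lets the treating physician reduce or hold as clinically indicated. It matters only as another way to reach DL-2.

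**Conclusion.** The point holds as an internal contradiction with a missing instruction. For a patient already at DL-2, after at least two earlier hematologic events or after Table 9 step reductions, Table 8 can name DL-1 while the text forbids re-escalation, and neither passage says whether the patient then remains at DL-2 or discontinues.

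The conflict appears under all three ways of counting hematologic events (56, 56 and 20 of 343 three-event paths; 0 of 49 two-event paths). It needs events of mixed grade or cell line, because three repeats within one row never name a higher dose. The counts describe the table and say nothing about how often patients will be affected. They rest on DL-1 and DL-2 being the levels of Tables 6 and 7 and on same dose meaning current dose.

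The effect is confined to Arm B (up to 20 patients). Sample size and the descriptive analysis of response rate are not touched. It is worth correcting because it is a dosing instruction that sites must apply.

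**What to change.** At the next amendment, reconcile Table 8 with the text of Section 7.3.1 and with Tables 6, 7 and 9. The protocol should state:

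1. that DL-1 and DL-2 are the levels of Tables 6 and 7, if that is meant;
2. how events are numbered: per row, per cell line or overall, and whether Table 9 events count;
3. what applies when Table 8 names a level above the patient's current one, and whether text or table takes precedence.

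Which clinical rule to adopt is for the sponsor; none is proposed here. The cost is a change of wording to one table and its accompanying text, with no extra patients, visits or data.
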